7.5.1.4 Duration of Response

[figure not shown]
DOR will be summarized using KM product-limit method. Median values of DOR based on KM method, along with two-sided 95%CI using Brookmeyer and Crowley method, will be calculated and presented in a table.

In addition, the percentage of subjects with ongoing response at different time points (3, 6, 12, 18, and 24 months) will be presented based on the DOR KM plot.

This analysis will be performed for all response evaluable subjects for all Cohorts, all intermediate/poor risk subjects and all favorable risk subjects only for Cohort 1 who achieve confirmed PR or CR.

A by-subject listing of TTR and DOR will be provided.

7.6 Safety

7.6.1 Primary Analyses

7.6.1.1 Incidence of High Grade Immune-Mediated Adverse Events

The number and percentage of subjects who report high-grade (Grade 3-4 and Grade 5) IMAEs will be summarized using all treated subjects. The IMAEs of interest are the followings: skin, endocrinopathy, gastrointestinal, hepatic, renal, pulmonary, and neurologic adverse events.

High grade (Grade 3-4 and Grade 5) IMAEs will be tabulated using worst grade per CTCAE v4.0 criteria by system organ class and Medical Dictionary for Regulatory Affairs (MedDRA) preferred term.

IMAEs are identified using a custom MedDRA query that is fully defined and updated by BMS and maintained as a separate file. The most recent version will be used for the analysis.

7.6.2 Secondary Analyses

7.6.2.1 Characterization of Outcome of High Grade Immune-Mediated Adverse Events

Time to onset and time to resolution will be analyzed for high grade (Grade 3-5) IMAEs of interest. The IMAEs of interest are the followings: skin, endocrinopathy, gastrointestinal, hepatic, renal, pulmonary, and neurological adverse events. Median values using the Kaplan-Meier (KM) product limit method with 95%CI using Brookmeyer and Crowley method will be presented for all treated subjects.

Analysis of endpoints related to management of high-grade (Grade 3-5) IMAEs will be conducted based on General Methods specified in [Section 7.1](#).

[Redacted]

[Redacted]

7.6.4 Laboratory Abnormalities

Laboratory abnormalities including hematology, chemistry, liver function, and thyroid function will be summarized using conventional units.

7.6.4.1 Hematology

See Section 7.6.10.1 of IO Core SAP.

7.6.4.2 Serum Chemistry

See Section 7.6.10.2 of IO Core SAP.

7.6.4.3 Electrolytes

See Section 7.6.10.3 of IO Core SAP.

7.6.4.4 Additional Analyses

See Section 7.6.10.4 of IO Core SAP.

7.6.5 Vital Signs and Pulse Oximetry

See Section 7.6.11 of CA209 Core Safety SAP.

[Redacted]

[REDACTED]

[REDACTED]

[REDACTED]

[REDACTED]

[REDACTED]

[REDACTED]

[REDACTED]

[REDACTED]

[REDACTED]

[REDACTED]

[REDACTED]

[REDACTED]

[REDACTED]

[REDACTED]

7.6.7 Pregnancy

See Section 7.6.15 of IO Core SAP.

7.6.8 Adverse Event By Subgroup

Not applicable.

[REDACTED]

[REDACTED]

[Redacted]

[Redacted]

[Redacted]

[Redacted]

[Redacted]

[Redacted]

[Redacted]

[Redacted]

[Redacted]

[Redacted]

[Redacted]

[Redacted]

[Redacted text block]

[Redacted text block]

[Redacted text block]

8 CONVENTIONS

Conventions are described in Section 8 of the IO Core SAP.

9 CONTENT OF REPORTS

9.1 Clinical Study Report

Statistical components for the clinical study report will be based on the content of this statistical analysis plan (SAP). Details of the tables, listings, and figures to be prepared for the final CSR will be included in a study-specific Data Presentation Plan (DPP).

9.2 Other Reports and Reviews

9.2.1 Safety Reviews

The safety review planned will include, but not be limited to the following frequency. Additional reviews may be triggered on an ad hoc basis by the BMS CA209-920 study team. Safety review for all treated subjects will take place, when any of the following criteria are satisfied:

- When a minimum of 5 subjects with KPS of 50-60% in Cohort 4 have received at least two combination doses therapy on study to assess safety and evaluate further enrollment into Cohort 4,

OR

- When a minimum of 10 subjects in Cohort 2-4 have received at least two combination doses therapy on study to assess safety and efficacy and evaluate further enrollment into the cohorts.

OR

- When a minimum of 25 subjects in Cohort 1 have received at least two combination doses therapy on study to assess safety and efficacy and evaluate further enrollment into Cohort 1.

According to the results of previous reviews, further monitoring and subsequent assessments and evaluation of safety and efficacy will be conducted according to the judgement of the BMS CA209920 study team, and data will be provided.

The following data will be provided for safety review:

- Subject disposition
- Demographic and baseline characteristics
- Exposure of study drug
- AEs with focus on:
 - Drug-related SAEs in all cohorts

- Immune-mediated adverse events all grades in all cohorts
- AEs leading to discontinuation
- All treatment-related deaths
- KPS over time.

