5.1.1 Data Monitoring Committee and Other External Committees

A Scientific Steering Committee (SSC) comprised of clinical experts in RCC will closely review the safety data throughout the study, especially for the special mRCC patient groups (Cohort 2, 3, and 4). The safety review plan will include, but not be limited to the following frequency. Additional reviews may be triggered on an ad hoc basis by the BMS CA209920 study team.

Safety review for all treated patients will take place, when any of the following criteria are satisfied:

- When a minimum of 5 patients with KPS of 50-60% in Cohort 4 have received at least two doses of combination therapy on study to assess safety and evaluate further enrollment into cohort 4,
- OR**
- When a minimum of 10 patients in Cohort 2-4 have received at least two doses of combination therapy on study to assess safety and efficacy and evaluate further enrollment into the cohorts.

OR

- When a minimum of 25 patients in Cohort 1 have received at least two doses of combination therapy on study to assess safety and efficacy and evaluate further enrollment into Cohort 1.

According to the results of previous reviews, further monitoring and subsequent assessments and evaluation of safety and efficacy will be conducted according to the judgement of the BMS CA209920 study team, and data will be provided.

The following safety data will be provided for safety review:

- Treatment-related adverse events with focus on:
 - Drug-related SAEs in all cohorts
 - Immune-mediated adverse events all grades, in all cohorts
 - AEs leading to discontinuation
 - All treatment related deaths
- KPS over time

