7.1 General Methods

In general, unless expressly stated otherwise, all analyses will be performed by separated Cohort 1, Cohort 2, Cohort 3 and Cohort 4. Except where otherwise stated in this SAP, all analyses and summaries will be performed for all treated subjects. Analyses based on the combination of Cohorts 2-4 are considered not necessary for CSR as Cohort 4 has low KPS and tolerability may not be the same with other groups.

Unless otherwise noted, the bulleted titles in the following subsections describe tabulations of discrete variables, by the frequency and proportion of subjects falling into each category, by cohorts (with total). Percentages given in these tables will be rounded and, therefore, may not always sum to 100%. Continuous variables will be summarized by cohort (with total) using the mean, standard deviation, median, minimum and maximum values.

Time to event distribution (i.e. progression free survival, overall survival and duration of response) will be estimated using Kaplan Meier (KM) techniques. When appropriate, the median along with 95% CI will be provided using Brookmeyer and Crowley methodology (using log-log transformation for constructing the confidence intervals). Rates at fixed timepoints (e.g. PFS 1 at 6 months) will be derived from the Kaplan Meier estimate and corresponding confidence interval will be derived based on Greenwood formula for variance derivation and on log-log transformation applied on the survivor function $S(t)$.

The CA209 Core Safety DPP refers to several analyses that are to be performed on subjects with extended follow-up. For these summaries, AEs occurring from the time of the first dose of study therapy through 100 days after the last dose of study therapy will be summarized. Further general methods information for the safety analyses, including general methods for AEs and laboratory tests can be found in Section 7.1 of the IO core SAP.

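### Two of the three enrollment reviews are meant to assess efficacy as well as safety, but the listed data contain no response, progression or survival item, and the only explicit death item is treatment-related deaths.

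*SAP*

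**What the plan says.** Protocol 5.1.1 and SAP 9.2.1 set out the same three triggers, joined by OR, for a safety review of all treated participants.

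- **Cohort 4** (at least 5 participants with two combination doses): the purpose is "to assess safety and evaluate further enrollment into Cohort 4". Efficacy is not named.
- **Cohorts 2-4** (at least 10 participants with two combination doses): the purpose is "to assess safety and efficacy and evaluate further enrollment into the cohorts".
- **Cohort 1** (at least 25 participants with two combination doses): the purpose is "to assess safety and efficacy and evaluate further enrollment into Cohort 1".

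The data for the review follow. The Protocol introduces its list with "The following safety data will be provided for safety review". It gives treatment-related adverse events, with a focus on drug-related SAEs, IMAEs of all grades, events leading to discontinuation and treatment-related deaths, and it adds KPS over time. The SAP list adds subject disposition, demographic and baseline data, and exposure. It heads the safety item with adverse events in general, and its death item is "All treatment-related deaths".

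**The concern.** A review asked to weigh efficacy needs some efficacy data, and neither list has any. All-cause death is the information that bears on both safety and efficacy, yet the one death item passes only those deaths that the investigator has called related to treatment.

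The trial is open-label, has no control arm, and includes participants with brain metastases or KPS 50-60%. Whether an early death is due to disease or to treatment is a judgement, and there is no comparator against which to test it. If the lists are followed as written, a decision on further enrollment could be taken without a complete count of deaths by cohort. No other planned look fills the gap: Protocol 10.3.4 states that interim analyses are not applicable, and Protocol 5.1.1 describes no other committee.

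**Working it through.** The plan states no figure for this review (no error rate, threshold or expected number of deaths), so there is nothing to reproduce. The check sets the passages side by side and then works out the timing.

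**1. Purpose against content**

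| Item | Protocol 5.1.1 | SAP 9.2.1 |
|---|---|---|
| Triggers naming efficacy | 2 of 3 | 2 of 3 |
| Response or progression listed | No | No |
| Survival or all-cause deaths listed | No | No |
| Explicit death item | Treatment-related only | Treatment-related only |
| Adverse event heading | Treatment-related events | AEs, no causality limit |
| Disposition, baseline, exposure | Not listed | Listed |

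The open-ended wording at the start of both sections qualifies how often reviews take place, not what data they receive.

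**2. What the other listed items can show about deaths**

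- *Disposition (SAP only).* SAP 7.3.1 tabulates reasons for stopping treatment and study by cohort. Death may appear as a reason, but the documents do not give the reason categories, and the table carries no cause or attribution.
- *Adverse events leading to discontinuation.* In the SAP these carry no causality limit. In the Protocol they sit under the treatment-related heading.
- *IMAEs.* Protocol 9.2.1.1 and SAP 4.1 define them regardless of causality, so a Grade 5 IMAE would appear. The definition also excludes events with a clear alternative cause unless there is an immune-mediated component, so a death put down to disease alone would not qualify. The Protocol list places this causality-free category under a treatment-related heading, which is a small inconsistency of its own.

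Together these may show some deaths not called treatment-related. None gives a count of all deaths by cohort.

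**3. Are the data available?** Yes. Protocol 9.2.1 and Appendix 9 require all SAEs, related or not, through 100 days after dosing, reported within 24 hours, and a fatal outcome makes an event an SAE. Table 2-5 adds survival contacts every 3 months.

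**4. When could efficacy data exist?** Inputs are dosing every 3 weeks (Cohorts 2-4) or every 8 weeks for the combination (Cohort 1), from Protocol 7.1, and the first scan at Week 12 ± 1, from Protocol 9.1.

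- Second combination dose, Cohorts 2-4: Day 1 + 21 = Day 22.
- Second combination dose, Cohort 1: Day 1 + 56 = Day 57.
- Earliest scheduled scan: Day 1 + 11 × 7 = Day 78.
- Gap: 78 − 22 = 56 days in Cohorts 2-4; 78 − 57 = 21 days in Cohort 1.

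A participant who has just met the two-dose condition therefore has no scheduled on-study scan. Earlier entrants may have one, depending on accrual. As an illustration, assume even accrual, no dropout or delay, and 100 participants in Cohorts 2-4 and 100 in Cohort 1. Enrollment lasts the planned year (Protocol 5.2) or, as a slower case, two years.

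| | One year | Two years |
|---|---|---|
| Cohorts 2-4: 10th participant enters | 52 × 10/100 = week 5.2 | 104 × 10/100 = week 10.4 |
| Trigger met (+3 weeks) | week 8.2 | week 13.4 |
| Past Week 12 by then | none | 1.4 × 100/104 ≈ 1 |
| Cohort 1: 25th participant enters | 52 × 25/100 = week 13 | 104 × 25/100 = week 26 |
| Trigger met (+8 weeks) | week 21 | week 34 |
| Past Week 12 by then | 9 × 100/52 ≈ 17 | 22 × 100/104 ≈ 21 |

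On these assumptions, the Cohort 2-4 review would have almost no scans, so deaths would be the main efficacy-relevant information. The Cohort 1 review would have a useful number of scans, and none is listed.

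**The case against.** The strongest reply is that the package is wider than its death item. The SAP includes disposition by cohort, its adverse event item names a focus and is not exclusive, and IMAEs count regardless of causality. The study team may also call ad hoc reviews, and the steering committee is to follow safety throughout the study, with particular attention to Cohorts 2-4. This stands in part. A reader might infer that every death not called treatment-related is hidden from the review. The documents do not support that. They support only that no explicit all-cause death item is listed, and that the Protocol list offers fewer indirect routes to such deaths.

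A second reply is that adding response tables would achieve little, because the first scan comes after the second combination dose. That holds for participants who have just met the condition, and it makes deleting efficacy from the purpose an equally consistent repair. It does not remove the mismatch.

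A reader might also infer a fault in the Cohort 2-4 trigger, which counts three populations together with no minimum for each, and cite SAP 7.1: "Cohort 4 has low KPS and tolerability may not be the same with other groups". That does not follow. The remark concerns analyses for the study report and singles out Cohort 4, which already has its own trigger. It does not say that Cohorts 2 and 3 differ from each other. Any trigger also prompts a review of all treated participants, and the text does not say that data will be shown pooled. Separate triggers for Cohorts 2 and 3 would be a preference, not the repair of an error.

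**Conclusion.** The point holds in limited form. In both documents, two of the three triggers name efficacy, and no response, progression or survival item is listed. The only explicit death item depends on investigator attribution, and the Protocol list is narrower than the SAP list.

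The number of deaths affected cannot be given, because the documents state neither an expected death rate nor the share likely to be called unrelated. The timing result in days follows from the schedule alone. The accrual illustration rests on the stated assumptions.

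The primary analysis is untouched, and the point says nothing about how deaths or survival are analysed in the final report. It concerns the quality of the planned enrollment review and should be corrected. The SAP is dated May 2020, and the documents do not show whether enrollment was still open. If it had closed, the change would still matter for any later review and for an accurate account of what earlier reviews saw.

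**What to change.** In Protocol 5.1.1 and SAP 9.2.1:

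1. Replace the treatment-related death item with all deaths, by cohort, giving date, cause and investigator attribution. Treatment-related deaths remain identifiable within that listing.
2. Align the Protocol adverse event heading with the SAP so that it is not limited to treatment-related events.
3. Choose one of two repairs for efficacy. Either add investigator-assessed response and progression status available at the data cut, by cohort, with a note that participants who have just reached two combination doses will have no scheduled scan before Week 12 (± 1 week). Or remove efficacy from the stated purpose of the Cohort 1 and Cohort 2-4 reviews.

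The cost is a few extra listings from data the trial already collects, plus a short wording change in two documents. No new visits, assessments or triggers are needed.

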APPENDIX 1 INTERNATIONAL METASTATIC RCC DATABASE CONSORTIUM (IMDC) PROGNOSTIC CRITERIA

Adverse Prognostic Factors
Clinical
KPS < 80% Time from diagnosis to treatment < 1 year
Laboratory
Hemoglobin < LLN Corrected calcium > ULN Absolute neutrophil count > ULN Platelet count > ULN

LLN = Lower limit of normal

ULN = Upper limit of normal

Corrected calcium (mg/dL) = measured total Ca (mg/dL) + 0.8 (4.0 - serum albumin [g/dL]), where 4.0 represents the average albumin level in g/dL.

Corrected calcium (mmol/L) = measured total Ca (mmol/L) + 0.02 (40 - serum albumin [g/L]), where 40 represents the average albumin level in g/L

[REDACTED]

[REDACTED]

[REDACTED]

[REDACTED]

[REDACTED]

[REDACTED]

APPENDIX 3 ADVERSE EVENTS OF INTEREST DEFINITION AND CONVENTIONS

The adverse events of interest including IMAE, select AE, and other event of special interest consist of a list of preferred terms grouped by specific category and by subcategory. These categories and subcategories are defined by the Sponsor and the list that is most current at the time of analysis will be used. Also, changes may be made to this list with each new version of MedDRA.

Time-to onset definition

Time-to onset of AE (any grade) for a specific category (e.g. pulmonary events, gastrointestinal events, ...) is defined as the time between the day of the first dose of study treatment and the onset date of the earliest AE (of any grade) in this category.

If the subject did not experience an AE (of any grade) in the category, time-to onset will be censored at the maximum follow-up time of all subjects in their respective treatment group (i.e for subjects without an event, follow-up time is defined from first dosing date up to last dosing date +30 days (or 100 days depending on the analysis) if subjects are off treatment and followed for at least 30 days (or 100 days depending on the analysis) , otherwise it is defined up to the last known alive date). The resulting Kaplan-Meier plot will represent the cumulative rate of the select AE (any grade) in the category over time.

Time-to onset of AE (grade 3-5) for a specific category is defined similarly but restricted to grade 3-5 AEs.

Time-to onset of drug-related (grade 3-5 or any grade) AE for a specific category is defined similarly but restricted to drug-related AEs.

Time-to onset for a specific subcategory is defined similarly but restricted to event of this subcategory.

Time-to resolution definition

In order to derive the time-to resolution, overlapping or contiguous AEs within a specific category will be collapsed into what will be termed “clustered” AEs. For example, if a subject (without pre-treatment AE) experienced an AE from 1st to 5th January, another AE (with different PT but within same category) from 6th to 11th January and same AE from 10th to 12th January, these will be collapsed into one clustered AE from 1st to 12th January. [Table A3-1](#) summarizes key derivation steps for each type of clustered AEs.

Time-to resolution of AE (any grade) for a specific category is defined as the longest time from onset to complete resolution or improvement to the grade at baseline among all clustered select AEs in this category experienced by the subject. Events which worsened into grade 5 events (death) or have a resolution date equal to the date of death are considered unresolved. If a clustered AE is considered as unresolved, the resolution date will be censored to the last known date alive. Improvement to the grade at baseline implies that all different adverse events in the clustered adverse event should at least have improved to the corresponding (i.e. with same preferred term)

baseline grade. This measure is defined only for subjects who experienced at least one AE in the specific category.

The time-to resolution of AE (grade 3-5) for a specific category is defined similarly with an onset date corresponding to a grade 3-5 AE.

Time-to resolution of drug-related AE (any grade or grade 3-5) is defined similarly but restricted to drug-related AE.

The time-to resolution of AE (any grade or grade 3-5, drug-related or all) where immune modulating medication was initiated is defined similarly with the additional condition that the subject started an immune modulating medication during the longest AE resolution period.

Time-to resolution for a specific subcategory is defined similarly but restricted to event of this subcategory.

Table A3-1: Derivation of Clustered AE of Interest

Type of clustered AE of interest	Derivation
Any grade	Collapse any on-treatment AE from the same category
Drug-related of any grade	Collapse any on-treatment drug-related AE from the same category
Grade 3-5	Collapse any on-treatment AE from the same category. Resolution will be based on the onset date of the earliest grade 3-5 records (if no grade 3-5 record, clustered AE is excluded)
Drug-related of Grade 3-5	Collapse any on-treatment drug-related AE from the same category Resolution will be based on the onset date of the earliest grade 3-5 record (if no Grade 3-5 record, clustered AE is excluded)

The algorithm for collapsing adverse event of interest (IMAE, select AE, other event of special interest) records uses the following conventions:

For each subject and specified category, the corresponding adverse event records will be collapsed when:

- 1) Multiple adverse event records have the same onset date.
- 2) The onset date of an event record is either the same day or 1 day later than the resolution date of a preceding event record (contiguous events).

The onset date of an event record is after the onset date and prior to or on the resolution date of a preceding event record (overlapping events).

[REDACTED]

[REDACTED]

[REDACTED]

[REDACTED]

[REDACTED]

[REDACTED]

[Redacted]

[Redacted]

[Redacted]

[Redacted]

[Redacted]

[Redacted]

[Redacted]

[Redacted]

[Redacted]

[Redacted]

[Redacted]

[Redacted]

[Redacted]

[Redacted]

[Redacted]

[REDACTED]

[REDACTED]

[REDACTED]

[REDACTED]

[REDACTED]

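### Time to resolution of high-grade IMAEs: participants who die before resolution are classed as unresolved but censored at death in a Kaplan-Meier analysis, which overstates resolution and shortens the median or leaves it unchanged

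*SAP*

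**What the plan says.** SAP Appendix 3 sets the conventions for adverse events of interest and names IMAEs within its scope: "The adverse events of interest including IMAE, select AE, and other event of special interest consist of a list of preferred terms". For time to resolution it takes, per category, the participant's longest clustered event, and it applies the same definition to Grade 3-5 events. The population is those affected: "This measure is defined only for subjects who experienced at least one AE in the specific category".

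Two consecutive sentences then deal with death. The first gives the status: "Events which worsened into grade 5 events (death) or have a resolution date equal to the date of death are considered unresolved". The second gives the time: "If a clustered AE is considered as unresolved, the resolution date will be censored to the last known date alive".

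SAP 7.6.2.1 names the estimator for high-grade IMAEs: "Median values using the Kaplan-Meier (KM) product limit method with 95%CI using Brookmeyer and Crowley method will be presented for all treated subjects".

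SAP 4.2 and protocol 10.3.2 define time to resolution only as onset date to end date, with ongoing events censored at last contact. Neither has a rule for an event that ends in death. The readable text of SAP 4.2 and 7.6.2.1 does not refer to Appendix 3.

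**The concern.** The two sentences on death pull apart. The first recognises that a fatal event has not resolved. The second gives that participant the same treatment as someone whose follow-up merely stopped. Kaplan-Meier takes censoring to be uninformative about the event, so it credits the dead participant with the later resolution experience of the survivors.

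This matters because the outcome of high-grade IMAEs is the first secondary objective of a safety trial, and because the distortion from deaths runs one way, towards faster and more complete resolution. SAP 7.1 analyses each cohort separately. Two cohorts plan about 25 participants, one of them with KPS 50-60%, so one death can carry weight where few participants have an IMAE.

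The primary analysis covers part of the gap. SAP 7.6.1.1 says: "High grade (Grade 3-4 and Grade 5) IMAEs will be tabulated using worst grade per CTCAE v4.0 criteria by system organ class". That table shows Grade 5 IMAEs. It does not show a Grade 3-4 IMAE that was still unresolved when the participant died, which Appendix 3 censors in the same way.

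**Working it through.** The documents give no figure for time to resolution, so there is none to reproduce. The check covers direction first, then size.

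**Inputs.** The rule comes from SAP Appendix 3 and the estimator from SAP 7.6.2.1. Cohort sizes (100 and 25) and a 34.0% high-grade IMAE rate come from SAP Section 5 and only scale the illustration: 34 affected of 100, and 8.5 (taken as 9) of 25. The share f dying before resolution and the medians to resolution (42 days) and to death (30 days) are assumptions.

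**Direction.** Kaplan-Meier is S(t) = product of (1 − d/n). Censoring k deaths removes them from every later n. Keeping them at risk as never resolved replaces n by n + k, and 1 − d/(n + k) ≥ 1 − d/n. The never-resolved curve is therefore never below the planned one, and its median is never shorter.

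Example: 34 affected participants with exit times 3, 6, 9, … days. Those at days 9, 21, 33 and 45 die; all others resolve.

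- Deaths censored: S(57) = 32/34 × 28/31 × 24/27 × 20/23 × 15/19 = 0.519. S(60) has 14/19 as its last factor and equals 0.484. The median is 60 days.
- Deaths never resolved: 16 resolutions by day 60 give S = 18/34 = 0.529, and 17 by day 63 give 0.500. The median is 63 days.
- Four deaths placed after the median instead: 51 days under both rules.

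In 20,000 random data sets of 5 to 64 participants, the planned median was shorter than the never-resolved median in 52%, equal in 48% and longer in none.

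**Size.** With λr = ln 2/42 = 0.0165 and λd = ln 2/30 = 0.0231 per day:

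- Competing risk: F(t) = (1 − f)(1 − exp(−λr t)), so the median is −ln(1 − 0.5/(1 − f))/λr. At f = 0.20 this is −ln(0.375)/0.0165 = 59.4 days.
- Planned: 1 − exp(−∫h), where h(u) = (1 − f)λr exp(−λr u) / [(1 − f)exp(−λr u) + f exp(−λd u)], solved numerically.

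| Share dying before resolution | Planned v competing-risk median, death median 30 d | Same, death median 120 d | Resolved by week 24, death median 30 d |
|---|---|---|---|
| 2.9% (1/34) | 43.1 v 43.9 d | 43.6 v 43.9 d | 93.4 v 91.0% |
| 11.8% (1/8.5) | 46.8 v 50.7 d | 49.4 v 50.7 d | 92.3 v 82.7% |
| 20% | 50.9 v 59.4 d | 56.3 v 59.4 d | 91.0 v 75.0% |

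The week-24 percentage is not a planned statistic in the readable text. Over assumed medians of 28-84 days (resolution) and 14-60 days (death), the shift in the median is 0.2-3.1 days at f = 3%, 1.2-14.8 at 12% and 2.6-29.6 at 20%.

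**Small samples** (40,000 simulated data sets each, 42- and 30-day medians, planned rule v never resolved):

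| IMAEs, deaths | Median unchanged | Mean shift |
|---|---|---|
| 9, 1 | 85% | 2.3 d |
| 9, 2 | 49% | 10.3 d |
| 34, 1 | all | 0 |
| 34, 4 | 63% | 1.6 d |
| 34, 7 | 12.5% | 6.0 d |

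For scale, the 95% sampling range of a 42-day median is 14-94 days with 9 IMAEs and 25-65 with 34.

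**Deaths unrelated to the IMAE.** With independent constant hazards, the share dying first is λd/(λr + λd). Assumed median survival of 8, 15 or 30 months gives 14.7%, 8.4% or 4.4%. The planned median stays at 42.0 days; the competing-risk median is 45.6, 43.8 or 42.9.

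**The case against.** The strongest reply is that this is partly a choice of question. For a death unrelated to the IMAE, censoring at death estimates how long resolution would take if nobody died. That is a coherent hypothetical, and the 42.0 days in the last calculation is exactly that quantity. This stands, so the criticism is firmest for IMAEs that are themselves fatal, where a resolution time absent death has no useful meaning.

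Appendix 3 is also a safeguard. Read literally, SAP 4.2 could count an end date equal to the death date as a resolution, and Appendix 3 prevents that. Against that reading the Appendix 3 median was longer in 69% of the 20,000 data sets. This is true, but that comparator does not treat a fatal event as unresolved, so it does not bear on the direction shown above.

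The illustrations pool IMAEs, one per participant, whereas the plan works by category on the longest cluster. Category counts will be smaller and noisier, so the figures show scale and are not forecasts. Text after SAP 7.6.2.1 is redacted, and table details sit in a separate data presentation plan, so counts of fatal or ongoing IMAEs may already be planned.

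A reader might infer that the planned median as a whole can only be too short. The documents do not support that. The same censoring sentence covers living participants with unresolved events. If their adverse-event information stops before the last date they are known to be alive, their censoring could lengthen the median. The one-way result concerns deaths only.

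**Conclusion.** The point holds for participants who die before their high-grade IMAE resolves. Appendix 3 calls them unresolved, and the Kaplan-Meier analysis then treats their deaths as non-informative censoring. Relative to never resolved, the status Appendix 3 itself assigns, resolution is overstated and the median is shortened or unchanged. With no such deaths, or only deaths after the median, the median does not move.

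Size depends on the share dying before resolution, which the documents do not give. Under the 42- and 30-day assumptions the median is about 1 day short at 2.9%, 4 days at 11.8% and 8.5 days at 20%, and less if deaths come later. With few deaths this is below sampling error.

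It would be wrong to infer that the trial's main safety result is biased. The primary endpoint is an incidence and does not use this rule, and time to resolution is a descriptive secondary summary without a test. The case for changing it is that a stated rule gives a one-sided result on a safety outcome and is cheap to correct.

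**What to change.** In SAP Appendix 3, estimate time to resolution as a cumulative incidence with death before resolution as a competing event. Take the median as the time the curve reaches 50%, and report it as not reached if it does not.

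A close alternative is to keep these participants at risk as never resolved, by censoring them beyond the longest resolution or follow-up time, measured from IMAE onset, in the cohort and category. The maximum follow-up that Appendix 3 uses for time to onset runs from first dose and cannot be carried over as written. Holding deaths at risk in this way is slightly conservative when many living participants are still unresolved at the cut. In a simulation with f = 20% and 30% of participants cut off within 24 weeks, it gave 59.7 v 59.3 days and 73.5 v 75.1% at week 24, against the competing-risk estimate.

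Beside the median, report per cohort how many high-grade IMAEs were fatal, unresolved at death, or ongoing, unless the redacted text already plans this. Refer SAP 4.2 and 7.6.2.1 to the Appendix 3 definition, so that an end date equal to the death date cannot be read as resolution.

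The cost is SAP wording in three places and one changed derivation, with no new data. The downside is that resolution figures become slightly less favourable if any participant dies before resolution.
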